progress and we expect to curate > 200 gene-disease pairs by the end of the NC NEXUS project. Scores, may be update periodically to reflect progress in the evidence base or advances in management of different genetic disorders. These scores will be used, in combination with curated information regarding the age of onset or age at which interventions would occur, to define the four categories of genomic information defined in this protocol. Since the development of final lists conditions in each of these categories is a primary outcome of the study, we anticipate that the work of binning each Mendelian disorder is expected to continue throughout the study period, and that periodic updates of the lists will occur. The FDA will be provided with a 5-day notice of any updates or changes in the lists that are implemented in the informatics algorithms.

Genetic Variant Interpretation and Reporting:

A member of the study team, acting as a molecular analyst, will conduct an initial review of the variant data, including review of quality metrics, visual inspection of variants, and review of the literature. The results of the analysis will be presented to the molecular sign-out committee (board-certified clinical geneticists, genetic counselors, clinical molecular geneticists and pathologists) for discussion. Final interpretations will be added as part of that variant's annotation in the database, so that future instances of that variant can be consistently assigned. The research team will review all variants identified as being possibly reportable (see below for detailed procedures). Those judged to be clinically relevant would be confirmed in the CLIA-certified MGL using the duplicate DNA sample.

Indication-based analysis

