Cases fulfilling these criteria will undergo review by a molecular analyst and the molecular sign-out conference, and only variants determined to be “known pathogenic” or “likely pathogenic” and consistent with the expected inheritance pattern would be returned in the context of NGS-NBS. All other cases will be reported as “negative.” This approach is an inherently conservative one. We recognize that the strict thresholds outlined above will inherently have imperfect sensitivity for detecting clinically relevant variants, but at the same time this approach will have higher specificity and therefore protect against false positive results. This is also a pragmatic approach, since it will be impossible for a human to comprehensively review each of the many variants that will be identified in every individual. Thus, the balance we are striving to achieve is to maximize clinical sensitivity and specificity, while minimizing the effort required of a human molecular analyst.

CLIA Confirmation:

All results deemed reportable in the NC NEXUS study will be confirmed by orthogonal methods (Sanger sequencing) in the CLIA-certified UNC Hospitals MGL (Mol Gen Custom DNA Sequencing, see Appendix 7). A clinical report will be generated and approved by a board-certified molecular geneticist or pathologist. This result will be provided to the parents and will be eligible to be included in the electronic health record (NC NEXUS NGS-NBS Electronic Medical Record (EMR): Appendix 20 and NC NEXUS Additional Results Electronic Medical Record (EMR) Consent: Appendix 21).

Randomization:

After sequencing and analysis of the indication-based analyses and/or NGS-NBS are complete, the couple will be randomized into a “decision group” or a “control group”. The couple will be contacted to arrange a return of results visit with a geneticist and genetic counselor.

Randomization will be computer implemented using permuted block randomization with blocks of randomly varying size. Participants will be stratified for block randomization based on three parameters: study cohort (“Diagnosed Cohort” or “Well- child Cohort”), language preference (“English” or “Spanish”), and the relationship status of the parent(s) giving consent (“Single” or “Couple”). In this way, we will achieve optimum randomization within each of these groups.

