- ***Previously unknown diagnoses:*** Participants in both the “Well-child cohort” and “Diagnosed cohort” will have the potential to receive positive findings from NGS-NBS or other additional categories of genomic information that will represent new information (i.e. unrelated to a diagnostic indication). These results will be provided to parents by a certified genetic counselor and MD medical geneticist, and a standard-of-care clinical follow-up plan will be established that is appropriate for the finding. This customized plan may involve long-term monitoring by a pediatrician, diagnostic imaging, other screening tests, and referral to specialists. This follow-up plan will be part of the patient’s clinical care. Clinicians associated with the NC NEXUS

study will serve as consultative resources for clinical providers but will not be directly responsible for the care of the patients. Study personnel will actively monitor the EHR as part of an observational study to track how genomic findings are utilized. In order to mitigate medical risks in this population, study providers will determine specific benchmarks (depending on the individual finding) that will be evaluated to ensure that appropriate follow-up is being given. Study personnel will track these benchmarks and, if a benchmark is not met, we will communicate with the parent to determine why and to develop an alternative clinical follow-up plan depending on the situation.

- **Negative results:** Most participants in the “Well-child cohort” and some participants in the “Diagnosed cohort” will have negative findings. Results will be provided to parents by a certified genetic counselor and MD medical geneticist, parents will be counseled regarding the small chance of a false negative result, and the patients will undergo routine clinical follow-up with their providers. Study personnel will passively monitor for rare cases of false negative genomic results by inviting parents to contact the study in the rare event that symptoms of a genetic disorder develop in their child.

Outcomes will be tracked in every participant by way of a chart review performed at the end of the study period. This review will include developmental outcomes, clinical events specific to any diagnoses, and results of any screening or diagnostic tests.

Indication-based reanalysis:

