Parental Decision Making Using Decision Aid. [Time Frame: average of 3-6 months.]

Analysis of parents' decisions after they complete an on-line decision aid to see if they wish to participate in the study. Parent participants randomized to the decision group, after their child is sequenced, may decide what, if any, additional categories of conditions they wish to learn about. Options will be yes, no, or unsure.

Sensitivity of Whole Exome Sequencing in Detecting Conditions by Comparing Results of Sequencing to the Appropriate Genes Associated With the Child's Underlying Condition. [Time Frame: approximately 3-6 months after DNA sample obtained.]

Investigators will analyze sequencing results in the diagnosed cohort to determine the ability of whole exome sequencing to detect pathogenic variants in genes related to phenotype.

Secondary Outcome Measures:

Participant Characteristics and Reactions to the Study Will be Collected Through Surveys. [Time Frame: Baseline and 3 months after final return of results visit.]

Surveys are administered at Time 1 (baseline), after parent participants decide to join phase I of the study, which involves agreeing to view the online decision aid about Next-Generation Sequencing Newborn Screening (NGS-NBS); at Time 2, after parent participants have viewed the decision aid and made a decision about accepting NGS-NBS for their child (yes/no/need more information; note that the timing is variable, depending on when participants complete this task, but may range from hours to weeks); at Time 2a (for parent participants randomly assigned to learn/make decisions about additional information), after parent participants have made the decision to accept none, some, or all categories of additional information (note that the timing is variable depending on when parent participants complete this task, but occurs after return of NGS-NBS results); Time 3, which occurs 2 weeks after return of NGS-NBS results; and Time 4, which occurs 3 months after Time 3.

Study endpoints

Primary Objective 1: Scientific endpoints for this objective will be a.) generation of whole exome sequence data and variant call files, b.) analysis of variants to determine whether any disease-causing variants exist, c.) confirmation of any suspected variants in the CLIA laboratory as a measure of analytic validity, and d.) comparison with clinical data to evaluate the sensitivity and specificity of sequencing.

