In addition, the study was designed to address the ELSI (Ethical, Legal, and Social Implications) research questions related to the impact of NGS on patients and their families. Using PASS software, we estimated the statistical power for a multiple regression model of mothers' mean scores predicting the decisional conflict scale with two predictor variables (study group [well- and diagnosed-child groups] and race/ethnicity [Black, White, and Hispanic]) and 10 control variables (e.g., demographics, health literacy, trust in medical community) that account for 20% of the variance in scores, assuming a p-value of 0.05. We assumed the sample would be split equally across racial/ethnic groups, consistent with the distribution in our study population. If study group and race/ethnicity account for 2% or more of the variance after controlling for the other variables, we will have statistical power of at least 82%, indicating acceptable power for comparisons by study group and race/ethnicity. We also examined power for detecting differences in decision to screen across study groups. We estimated power for a logistic regression comparing decision to screen between the two study groups, assuming the well-child group has approximately 70% probability of accepting NGS-NBS (based on our Fragile X NBS study) and using a p-value of 0.05. On the basis of these assumptions, we would have 83% power or higher to detect at least a 12% difference in probability of agreeing to screening between the two study groups, which corresponds to an odds ratio of 2.0.

Outcome data and data analysis

Primary Objective 1:

- A. Generation of whole exome sequence data: Datasets will include raw FASTQ short read files, aligned BAM files, and VCF variant call files. Variants will be annotated and deposited in a local database as described in section 2.
- B. Analysis of variants: Curated clinical significance of individual variants will be stored in the annotated database. Final case-level results (according to Table 2) for each patient will be recorded. Types of mutations that are detected will be characterized in aggregate.
- C. CLIA confirmation: Results from NGS will be compared with Sanger results in the CLIA lab to assess the false positive rate (analytic specificity) of NGS.
- D. Clinical sensitivity and clinical specificity: Calculations of test sensitivity and specificity will be performed based upon the diagnostic result and the clinical follow-up.

Primary Objective 2:

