 - the deviation was necessary to protect a subject from immediate harm
- **Breach of confidentiality**

Reporting Process

The reportable events noted above will be reported to the IRB using the form: “Reportable Event Form” or as a written report of the event (including a description of the event with information regarding its fulfillment of the above criteria, follow- up/resolution and need for revision to consent form and/or other study documentation).

Copies of each report and documentation of IRB notification and receipt will be kept in the Clinical Investigator’s study file.

Withdrawal of subjects from the study

The informed consent materials will clearly state that parents can withdraw from the study at any time, that this will not impact the child's medical care in any way. Parents who refuse to use the decision aids or fail to comply with the questionnaires will be considered withdrawn and their child’s sample will not undergo further sequencing or analysis. They will not participate in the randomization. Specimens from parents who desire to terminate participation will be destroyed and no further analysis of data in such individuals will be pursued.

Description of Investigational Device

On August 27, 2014, the FDA provided a response to a pre-submission inquiry and determined that the proposed NC NEXUS study would be required to submit an Investigational Device Exemption (IDE) due to the significant risk associated with the potential long-term consequences to both the parent(s) (i.e., psychological impact) and the child (i.e., denial of life and/or long-disability insurance and having medical records containing WES information of which he/she did not consent to) after learning of the WES finding. The FDA has determined that the decision aid that will be developed and the psychosocial research that will be conducted are also part of the “device” that is being evaluated. In that case, the “device” would be best described as:

“Informed parental decision-making aided by an electronic decision aid regarding their acceptance of next-generation sequencing newborn screening for their child; whole exome sequencing with targeted analysis and Sanger confirmation of positive findings; return of results through standard-of-care genetic counseling; and follow-up questionnaires regarding the psychosocial impact of the screening.”

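### Sanger testing of curated NGS-positive calls gives a confirmation proportion (analytic PPV), not the false positive rate or analytic specificity that item C names

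*Combined protocol and SAP*

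**What the plan says.** Under *Outcome data and data analysis*, Primary Objective 1, item C (CLIA confirmation) reads: "Results from NGS will be compared with Sanger results in the CLIA lab to assess the false positive rate (analytic specificity) of NGS".

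Four other places say what goes to Sanger:

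- *Genetic Variant Interpretation and Reporting*: an analyst reviews quality metrics, inspects variants visually and checks the literature, and a sign-out committee then discusses the case. "Those judged to be clinically relevant would be confirmed in the CLIA-certified MGL using the duplicate DNA sample".
- *CLIA Confirmation*: "All results deemed reportable in the NC NEXUS study will be confirmed by orthogonal methods (Sanger sequencing) in the CLIA-certified UNC Hospitals MGL".
- *Study endpoints*, Primary Objective 1(c): "confirmation of any suspected variants in the CLIA laboratory as a measure of analytic validity".
- *Description of Investigational Device*: "whole exome sequencing with targeted analysis and Sanger confirmation of positive findings".

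On negatives, *NGS-NBS and Additional Genomic Findings* says of cases outside the return criteria: "All other cases will be reported as" negative. Their follow-up is clinical: "Study personnel will passively monitor for rare cases of false negative genomic results by inviting parents to contact the study".

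**The concern.** Item C names one quantity and the design supplies the data for another. A false positive rate in the sense of specificity is conditional on the variant being truly absent, so it needs sites where NGS made no call as well as sites where it made a wrong one. The Sanger sample is conditional on NGS having made a call. It is narrowed further by computational class, quality review, visual inspection and committee judgement, so artefacts that a reviewer can recognise are largely removed before Sanger sees them.

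Two things are at stake. First, a reader of the results would take one minus the unconfirmed share as the specificity of NGS and might compare it with true specificities from elsewhere. Second, the figure would be attributed to NGS as a whole when it describes the output of NGS plus filtering plus expert curation. Analytic validity is a named endpoint of Primary Objective 1, so the quantity should be labelled correctly.

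**Working it through.** The documents give no value, target or precision for this measure, so there is no figure to reproduce. The check is whether the named quantity can be identified from the planned data.

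**Step 1: definitions.** Cross-classify each tested site by NGS (variant called or not) and Sanger (variant present or not).

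- Specificity = TN/(TN+FP), and false positive rate = FP/(TN+FP) = 1 − specificity.
- Positive predictive value = TP/(TP+FP), and unconfirmed proportion = FP/(TP+FP) = 1 − PPV.

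**Step 2: which cells are filled.** All four descriptions of the Sanger step concern NGS-positive findings, so TP and FP are observed and TN and FN are empty. I looked for anything that would fill them:

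- The statement under *False positive results* that all results are Sanger-confirmed is about keeping technical false positives from being returned, so it also concerns positives.
- Site-specific testing of relatives serves phase and interpretation, and no exome is described for relatives, so it gives no NGS–Sanger pair.
- Item D (clinical sensitivity and specificity) uses the diagnostic result and clinical follow-up. It is a separate calculation.

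No section plans Sanger at NGS-negative sites, in NGS-negative children, or in a random sample of calls.

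**Step 3: what the planned data give.** Taken literally from the verified sites, specificity is 0/(0+FP). That is 0 if any call fails and undefined (0/0) if none does. Assume for illustration that 4 of 200 calls are unconfirmed. Specificity then depends wholly on the unobserved TN:

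- TN = 10: 10/14 = 71.4%
- TN = 100: 100/104 = 96.2%
- TN = 1,000: 1,000/1,004 = 99.6%
- TN = 100,000: 100,000/100,004 = 99.996%

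The unconfirmed proportion is 4/200 = 2.0% in every row.

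**Step 4: what can be estimated, and how precisely.** Exact (Clopper-Pearson) 95% intervals for the unconfirmed proportion, with assumed counts and calls treated as independent:

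- 2 of 100: 2.0% (0.2% to 7.0%)
- 4 of 200: 2.0% (0.5% to 5.0%)
- 8 of 400: 2.0% (0.9% to 3.9%)
- 0 of 100: upper limit 3.6%
- 0 of 200: upper limit 1.8%

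**Step 5: how selected the tested calls are.** The *Bioinformatics* section gives about 100,000 variants per exome. Over 400 children that is 100,000 × 400 = 40 million calls. If 100 to 800 calls were Sanger-tested (assumed), the tested share is 100/40,000,000 = 0.00025% to 800/40,000,000 = 0.002%, and it is not a random share.

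**Step 6: unit of analysis.** One child can contribute several tested calls. A recessive finding can involve two variants, and the schedule of activities expects carrier status for 1–4 conditions as the most typical additional result. Calls within a child share one DNA sample and one sequencing run, so they are not obviously independent.

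**The case against.** The best defence is that item C is loosely worded rather than wrong in intent. Under *False positive results* the protocol describes technical false positives as erroneous variant calls, which is call-level language. Beneath a heading on CLIA confirmation, false positive rate could simply mean the share of tested calls that fail. Endpoint 1(c) is worded correctly and claims no specificity. The study is exploratory, the sequencing entry among the primary outcome measures is sensitivity in the diagnosed cohort, and the same Sanger data are collected whatever the statistic is called.

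Most of this stands, and it limits the severity. It does not rescue the text. The parenthesis equates the quantity with analytic specificity, no denominator is given, and the result is attributed to NGS without mention of curation. The protocol elsewhere treats PPV and specificity as different things, noting that the first depends on the second.

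Three stronger readings are tempting, and the documents do not support them:

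- *A 2% unconfirmed share implies a 2% error rate per base.* The protocol's language is about calls, no section gives a per-base denominator, and any such illustration needs an assumed target size.
- *Specificity can be recovered from the non-variant bases in the Sanger reads already made.* Those regions are tested only because NGS called a variant there, the answer depends on amplicon length, and nothing in the text shown establishes that full traces are kept in scorable form.
- *The IDE makes this critical.* The stated reason for the IDE is psychological impact on parents and insurance and medical-record consequences for the child, not analytic specificity.

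**Conclusion.** The point holds as a should-fix correction. As written, item C promises an analytic specificity that the planned data cannot identify. What can be estimated is the Sanger confirmation proportion of curated, reportable NGS calls. This conclusion rests only on where Sanger is applied and not on the illustrative counts, all of which are assumed.

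Specificity could be approximated if the plan fixed the number of interrogated reference sites, took false negatives as negligible and assumed that verified calls represent all calls. It states none of these.

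A reader might infer that families could receive wrong results or that a trial conclusion is at risk. Neither follows. Reportable results are confirmed before return, which guards against technical errors however the statistic is named, and no hypothesis, threshold or sample size uses this figure. The harm is confined to a mislabelled and over-generalised performance figure for one endpoint of Primary Objective 1.

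**What to change.** In item C, delete the reference to a false positive rate and analytic specificity, and state the quantity as: *the Sanger confirmation proportion (analytic positive predictive value) of curated reportable NGS calls, with an exact 95% CI, the unit of analysis stated, and allowance for more than one call per child.* One simple way to make that allowance is to report the per-call proportion together with the proportion of children with at least one unconfirmed call, the latter with its own exact interval. Add that the figure applies to calls that passed filtering and review, not to NGS calling in general.

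This changes one or two sentences, needs no new assay and brings item C into line with endpoint 1(c).

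Claim no specificity unless the plan defines a reference sample that includes NGS-negative sites, with weighting back by the sampling fractions if sites are chosen by NGS status. That would mean extra testing. In a simple random sample of sites where the reference shows no variant, zero NGS calls in 100, 300 or 1,000 sites gives an upper 95% limit on the false positive rate of 3.6%, 1.2% or 0.37%. The renaming does not depend on this option.

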Complete Title: NC NEXUS: North Carolina Newborn Exome Sequencing for Universal Screening

Short Title: NC NEXUS

Drug or Device Name(s): N/A

FDA IND/IDE (if applicable): IDE# G150258

Sponsor: NIH

Protocol Date: 06/18/2013

NCT Number: NCT02826694

Sponsor

National Institutes of Health
[name]
[name]
USA

Study Principal Investigator [name]

Division of Pediatric Genetics and Metabolism

[name]

[name]

[name]

[contact]

email: [contact]

1. Clinical Protocol

Title of Clinical Protocol

Short Name: The NC NEXUS Study

Long Name: The North Carolina Newborn Exome Sequencing for Universal Screening Study

Study Design

General Study Design

The NC NEXUS project is an exploratory longitudinal cohort study, with randomization of enrolled parents into two groups with different opportunities for decision-making about categories of non-medically actionable genomic information.

Cohorts:

We will enroll parents and their eligible child into the following 2 cohorts:

The “Diagnosed Cohort”: Our goal is to sequence 200 children from this cohort including infants and children up to age 5 who have metabolic disorders such as phenylketonuria (PKU) and medium chain acyl-CoA-dehydrogenase deficiency (MCADD); cystic fibrosis (CF) and *CFTR*-related metabolic syndrome (CRMS); congenital hearing loss; primary ciliary dyskinesia, and a variety of other rare conditions.

The “Well-Child Cohort”: Our goal is to sequence 200 infants whose parents enroll prenatally. The expectant mothers must be pregnant with an intrauterine pregnancy of 18 weeks or greater, have no pending or positive prenatal diagnostic test results for congenital malformations or chromosomal abnormalities and have been identified by medical personnel in the obstetrics clinic as possible candidates.

We will consider requests from couples who receive their OB care elsewhere but who have had consultations with the UNC prenatal clinic on a case-by-case basis.

Randomization:

In order to assess the impact of the additional non-medically actionable genomic findings available upon request, parents will be randomized in a 2:1 ratio to “Decision” or “Control” groups, respectively. Both groups will learn any childhood onset medically actionable results (“NGS-NBS”) from genomic sequencing at their return of result visit.

Study design narrative:

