- A. Clinical actionability curation: Curated literature review data for each gene-disease pair will be stored in a REDCap database. Final scores determined by the binning committee will be recorded and analyzed.
- B. Definition of categories of genomic information: Based on curation of age of onset and actionability, the binning committee will determine thresholds that define the four categories of genomic information as described in section 2.
- C. Observational study of outcomes and integration of findings into clinical

care: Longitudinal outcomes data will be collected in a REDCap database and analyzed.

Primary Objective 3:

Consistent with the primary research questions for this objective, which focus on ethical use of NGS-NBS, we specify the following primary independent variables: Race/ethnicity (non-Hispanic White, Black, Hispanic), health literacy, and child status (diagnosed vs. well). We specify the following primary dependent variables: sequencing-related distress, knowledge about NGS-NBS and (for the “decision group” only) about additional genomic results (continuous variables), decision to accept or decline NGS-NBS and (for the “decision group” only) additional genomic results (dichotomous variables), and decisional conflict (a continuous variable). Primary analyses will focus on these outcomes in mothers. These analyses involve a between-within design and will be analyzed with mixed linear modeling to accommodate nesting (i.e., assessments nested within participants). Models with continuous outcomes will be implemented with SAS PROC MIXED because (a) it can handle nested data; (b) it handles missing data more appropriately than repeated-measures analysis of variance, which uses listwise deletion of missing data; and (c) it provides a wider range of options for modeling the error covariance structure than general linear model procedures, which assume an error structure that is often unrealistic. Models with dichotomous outcomes will be implemented using mixed-effects logistic regression within SAS PROC GENMOD, which shares strengths similar to those offered by PROC MIXED.

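### Families are randomised 2:1 to Decision or Control, but no planned analysis compares the two arms

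*Combined protocol and SAP*

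**What the plan says.** The purpose of the randomisation is explicit in Study Design, Randomization: "In order to assess the impact of the additional non-medically actionable genomic findings available upon request, parents will be randomized in a 2:1 ratio". The Randomization paragraph in section 2 adds the timing, "After sequencing and analysis of the indication-based analyses and/or NGS-NBS are complete, the couple will be randomized", and the method: permuted blocks, with cohort, language preference and relationship status as stratification factors.

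The only model specification is under Primary Objective 3 in section 5, Outcome data and data analysis. On predictors it reads: "we specify the following primary independent variables: Race/ethnicity (non-Hispanic White, Black, Hispanic), health literacy, and child status (diagnosed vs. well". On outcomes it begins: "We specify the following primary dependent variables: sequencing-related distress, knowledge about NGS-NBS and (for the “decision group” only) about additional genomic results". It then adds the decisions on NGS-NBS and on additional results, and decisional conflict. Continuous outcomes go into PROC MIXED with assessments nested within participants, and the primary analyses are in mothers.

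Follow-up is common to both arms. All parents are to complete Time 3 and Time 4 after results are returned. Time 2A goes to the Decision arm only.

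**The concern.** The Control arm exists to show what parents' experience would be without the offer of additional findings. Cohort, race/ethnicity and health literacy are observational predictors, and none of them answers that question. In the Objective 3 text the randomised arm appears only as a restriction on which parents contribute certain outcomes. That describes the Decision arm and compares nothing.

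The question is not marginal to the protocol. The risk analysis says the risks of disclosing additional findings to the Decision group are unknown. The device description reports that the FDA required an IDE partly because of possible psychological impact on parents. If the outcome, time point and model for the arm contrast are not fixed in advance, whoever analyses the data later can choose among several outcomes and two follow-up times. The result would then carry the weight of a post hoc finding, although the allocation was randomised.

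**Working it through.** **1. Where an arm comparison could appear (all in section 5)**

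- Primary and Secondary Outcome Measures: parental decisions, sequencing sensitivity and surveys over time. The Decision group is mentioned only as making extra choices or receiving Time 2A. There is no contrast with Control.
- Study endpoints, Primary Objective 3: consent and decision events, return of variants and completion of measures. There is no contrast.
- Sample size determination: two power statements. The term study group is defined there as well-child v diagnosed-child, so it is not the randomised arm.
- Outcome data and data analysis, Primary Objective 3: three primary predictors, none of them arm.

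**2. The plan's own power figures, to confirm which contrasts they cover**

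Inputs are from Sample size determination. N = 400 (200 per cohort) is from Anticipated Number of Research Subjects. The power paragraph does not repeat it, so its use here is an assumption.

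- Regression on decisional conflict: f² = 0.02 / (1 − 0.20 − 0.02) = 0.0256, and noncentrality = 400 × 0.0256 = 10.26. With 2 tested degrees of freedom and alpha 0.05, power is 82.3%, against at least 82% stated. (Coding race/ethnicity with 2 degrees of freedom, 3 tested in all, gives 76.8%. That is a separate matter.)
- Logistic model: odds 0.70/0.30 = 2.333; times 2.0 = 4.667, a probability of 82.4%. With 200 v 200 and two-sided 0.05, power is 82.9%, against 83% stated. At exactly 12 points (70% v 82%) it is 80.5%.

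Both figures reproduce as cohort or race/ethnicity contrasts. The document has no power figure for Decision v Control.

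**3. What the planned sample offers for the arm contrast**

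Inputs: 2:1 allocation, one mother per family, two-sided 0.05, 80% power. The detectable difference in SD units is (1.960 + 0.842) × √(1/n_Decision + 1/n_Control).

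- 400 analysed (266.7 v 133.3): 2.802 × √(0.00375 + 0.00750) = 2.802 × 0.1061 = 0.297.
- 360 analysed (240 v 120): 2.802 × √(0.00417 + 0.00833) = 2.802 × 0.1118 = 0.313.

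The 360 case takes 5% + 5% = 10% off 400. It applies to both cohorts the dropout that the protocol gives in its well-child paragraph.

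| True difference | Power, N = 400 | Power, N = 360 |
|---|---|---|
| 0.2 SD | 47% | 43% |
| 0.3 SD | 80.7% | 76.5% |
| 0.5 SD | 99.7% | 99.4% |

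The risk analysis uses 0.5 SD as a meaningful change, but for decision regret, not distress.

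**4. Which outcomes an arm term can serve**

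Randomisation follows sequencing, so it follows the decision on NGS-NBS. Arm cannot explain that decision. Decisions and knowledge about additional results exist in one arm only. Sequencing-related distress at Times 3 and 4 is the natural lead: it is already a primary dependent variable, and the risk analysis says distress (depressive symptoms, anxiety) is collected before and after return of results. NGS-NBS knowledge is a further candidate. Whether decisional conflict is measured in both arms after randomisation depends on Appendix 19, which was not available.

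**5. The Time 4 anchor**

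The study design narrative and Follow-up Questionnaires place Time 4 at 3 months after the return of result visit. Secondary Outcome Measures places it at 3 months after Time 3, while the time frame there is 3 months after the final return visit. Only Decision families can have Visit 3, about 1 to 2 months after Visit 2. Under the final-visit reading, Control families would be assessed 3 months after Visit 2, and Decision families with a Visit 3 at 3 + 1 to 3 + 2, or 4 to 5 months. Arm and elapsed time would then be confounded.

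**The case against.** The strongest reply is that this is declared an exploratory longitudinal cohort study, and that the Objective 3 questions concern ethical use of NGS-NBS, which both arms receive. Cohort, race/ethnicity and health literacy are legitimate primary predictors for those questions. That stands, and it is why the arm contrast need not displace them. It does not excuse the gap. The plan names primary variables, models and power for observational contrasts while leaving out the comparison for which it randomises.

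Four stronger readings are tempting, and the documents do not support them.

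- *The randomised question cannot be answered.* Both arms are followed at Times 3 and 4, so the data would exist. What is missing is a prespecified analysis.
- *The withdrawal rule removes randomised families, mainly from the Decision arm.* The rule reads "Parents who refuse to use the decision aids or fail to comply with the questionnaires will be considered withdrawn", and the second aid and Time 2A are Decision-only. But the text goes on to stop further sequencing and analysis of the sample and to say such parents do not enter the randomisation, which points to a rule applied before allocation. Use of the second aid is only encouraged, and late responders may be offered a telephone interview. The plural 'aids' leaves some ambiguity, but the documents give no basis for sizing a bias.
- *Language and relationship status are left out of every model.* They are only not named. The power paragraph allows 10 control variables and gives examples, demographics among them.
- *Decision regret should be a primary arm outcome.* It is not among the primary dependent variables. Control parents never choose among additional categories, so their regret may not be like-for-like with that of Decision parents.

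**Conclusion.** The point holds as a missing prespecified analysis: the plan states why it randomises and then specifies no comparison of the randomised arms. This is more than absent detail, because the models and power statements given address other contrasts. The planned sample would detect about 0.30 SD with 400 families, or 0.31 SD with 360, and has under 50% power at 0.2 SD. These figures assume one mother per family, 2:1 allocation achieved, a single time point, no covariate gain, two-sided 0.05, and that all 400 (or 360) families are randomised and analysed. The 400 may already be net of dropout, since the protocol describes it as the number completing. The finding does not rest on any claim about differential withdrawal.

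**What to change.** In Outcome data and data analysis, Primary Objective 3:

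- Add a named Decision v Control comparison for post-randomisation outcomes that both arms complete, led by sequencing-related distress. It can stand beside the existing primary variables.
- Use the planned PROC MIXED model with arm, time, arm-by-time, the pre-randomisation distress value where collected, and cohort, language and relationship status. Analyse every randomised family as randomised.
- Name one time point for the contrast. Reconcile the conflicting Time 4 definitions to a single anchor that applies identically in both arms.
- In Sample size determination, state the detectable difference: about 0.30 SD with 400 families, 0.31 SD with 360.
- Optionally, add a sentence to Withdrawal of subjects from the study confirming that the rule on decision aids and questionnaires applies before randomisation.

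The cost is wording. No additional families are needed. For distress no new data collection is expected, subject to checking against Appendix 19 that the same scale is given to both arms at the chosen time.
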